2. INVESTIGATION PLAN

2.1. Study Design

This is an open-label, single armed study designed to evaluate the long-term safety and efficacy of evinacumab in patients with HoFH.

Eligible patients for this study are male and female patients with HoFH, receiving LMT, as applicable. Lipid modifying therapies may include maximally tolerated statin, ezetimibe, PCSK9 inhibitor antibody, or other lipid lowering therapies, including lipoprotein apheresis. Patients include those who have participated in a previous evinacumab study (i.e., R1500-CL-1331 and R1500-CL-1629) and evinacumab-naïve patients with HoFH.

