4.8.3. Vital Signs

Vital signs parameters will include height (cm), weight (kg), heart rate (bpm), respiration (rpm), temperature (C or F), systolic and diastolic blood pressure (mmHg) after resting at least five minutes. Both actual test values and “change from baseline” values (defined as the post-baseline value minus the baseline value) will be provided for protocol specified visits and visits will be assigned to the Global Analysis Windows (See Appendix 10.2). Potentially clinically significant

values (PCSV) ranges will be applied to the vital sign parameter values as applicable (see Appendix 10.4 for PCSV definitions).

4.8.4. 12-Lead Electrocardiography (ECG)

Electrocardiograms will be performed before blood samples are collected at visits requiring blood draws. A standard 12-lead ECG will be performed at specified time points according to Appendices 10.5 and 10.6. The ventricular rate, PR, QRS, RR, QT, QTcF, and QTcB intervals will be recorded. Electrocardiogram assessments will be described as normal or abnormal, and visits will be assigned to the Global Analysis Windows (See Appendix 10.2).

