5. STATISTICAL METHODS

In general, data will be summarized and presented in three patient groups, depending on the status of previous evinacumab treatment exposure:

- Continue Evinacumab: Patients who received evinacumab in a previous study (eg, R1500-CL-1331 or R1500-CL-1629);
- New Evinacumab: Patients without previous exposure to evinacumab (ie, evinacumab naïve);
- Total: All patients, regardless of previous (or not) evinacumab exposure.

These 3 evinacumab exposure groups will be provided for all patients in the respective patient analysis sets. Assuming there are enough adolescent patients (age ranging from 12 years to < 18 years old) to perform an evaluation, the three evinacumab treatment exposure groups will be provided again for the subpopulation of adolescent patients [yes/no]. The subpopulation of adolescent patients has two categories, specifically the patient is an adolescent defined as ranging in age from 12 years to < 18 years old, or the patient is not an adolescent (i.e. an adult) defined as ≥ 18 years of age. Unless otherwise noted, data from both adolescent and adult patient subgroups will be summarized.

Continuous data will be summarized descriptively using the number of patients with data, mean, SD, median, minimum and maximum for each patient group for the study. First quartile (Q1) and third quartile (Q3) will be also provided for baseline lipid parameters, HbA1c, and hs-CRP.

Categorical and ordinal data will be summarized using the number and percentage of patients for each patient group for the study.

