5.1. Demographics and Baseline Characteristics

Demographic and baseline characteristics will be summarized descriptively by patient group for the study in the safety analysis set.

Parameters listed in Section 4.1 will be summarized as described. As applicable, other safety baseline data not listed in Section 4.1 will be presented collectively in the descriptive statistics summary tables containing respective post-baseline data.

The summary of demographic and baseline characteristics will be provided for all patients in the study in the safety analysis set, and again for the subpopulation of adolescent patients.

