5.7.1. Analyses of Efficacy Variables

The observed percent and absolute change in lipid parameters (e.g., LDL-C, Apo B, TG, etc.) will be descriptively summarized for each visit, and by patient group for the study for patients in the SAF, and again for the subpopulation of adolescent patients for patients in the SAF. A within-patient t-test (lipids with a normal distribution) or Wilcoxon signed-rank test (non-parametric test for lipids with a non-normal distribution such as TG) will be provided for secondary efficacy endpoints to descriptively compare each patient's week 24 assessment to their baseline assessment. Missing data will not be imputed.

Unless otherwise specified, the baseline value used for determining percent and absolute change for each patient is defined as follows (also see in Section 6.1).

- For patients who participated in previous evinacumab study R1500-CL-1629, baseline is defined as the last obtained value before the first dose of double-blind study drug in R1500-CL-1629.
- For patients who participated in previous evinacumab study R1500-CL-1331 or did not participate in any previous evinacumab study, baseline is defined as the last obtained value before the first dose of study drug in R1500-CL-1719 (Note: Baseline for patients who participated in R1500-CL-1331 is defined as the baseline from the R1500-CL-1719 study due to the long time between the last study treatment in R1500-CL-1331 and the first study treatment in R1500-CL-1719).

For patients who participated in previous evinacumab study R1500-CL-1629 and received evinacumab in the DBTP, a combined summary of LDL-C including both the DBTP and OLTP assessments in R1500-CL-1629 study and the assessments in R1500-CL-1719 study (i.e., with DBTP first dose date in R1500-CL-1629 study as starting point) will be considered, referencing the double-blind baseline for variable calculations.

For patients who participated in previous evinacumab study R1500-CL-1629 and received placebo in the DBTP but received evinacumab in the OLTP, a combined summary of LDL-C including OLTP assessments in R1500-CL-1629 study and the assessments in R1500-CL-1719 study (i.e., with OLTP first dose date in R1500-CL-1629 study as starting point) will also be considered, referencing the double-blind baseline for variable calculations.

A combined summary of LDL-C assessments when receiving study R1500-CL-1629 evinacumab in the DBTP and OLTP for the above two groups of patients will also be considered.

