5.8.4. Analysis of Vital Signs

The vital sign actual values and change from baseline values obtained while sitting will be descriptively summarized at baseline and each post-baseline visit for the open-label treatment (OLTP) period, by at least patient number, mean, median, Q1, Q3, SD, minimum and maximum. Vital signs mean changes from baseline, with the corresponding SE, can be plotted at each visit in the case results warrant further investigation.

Individual patient vital sign measurements (regardless of sitting position) will be additionally evaluated by PCSV criteria, specifically identifying patients with at least one post-baseline measurement that meets the PCSV criteria within the TEAE period. The incidence of PCSVs at any time during the TEAE period will be summarized regardless of the baseline level, and again according to the following baseline categories:

- Normal (according to PCSV criterion/criteria)/missing
- Abnormal according to PCSV criterion or criteria

Patient listings of vital sign measurements that meet PCSV criteria will be provided for the report appendix.

The summary of vital signs will be provided for all patients in the study in the safety analysis set, and again for the subpopulation of adolescent patients.

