6.1. Definition of Baseline for Efficacy/Safety Variables

Unless otherwise specified, the baseline value used for determining percent and absolute change for each patient is defined as follows:

- For patients who participated in previous evinacumab study R1500-CL-1629, baseline is defined as the last obtained value before the first dose of double-blind study drug in R1500-CL-1629
- For patients who participated in previous evinacumab study R1500-CL-1331 or did not participate in any previous evinacumab study, baseline is defined as the last obtained value before the first dose of study drug in R1500-CL-1719 (Note: Baseline for patients who participated in R1500-CL-1331 is defined as the baseline from the R1500-CL-1719 study due to the long time between the last study treatment in R1500-CL-1331 and the first study treatment in R1500-CL-1719).

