HR	≤ 50 bpm and decrease from baseline ≥ 20 bpm ≥ 120 bpm and increase from baseline ≥ 20 bpm
SBP	≤ 95 mmHg and decrease from baseline ≥ 20 mmHg ≥ 160 mmHg and increase from baseline ≥ 20 mmHg
DBP	Young and elderly patients ≤ 45 mmHg and decrease from baseline ≥ 10 mmHg ≥ 110 mmHg and increase from baseline ≥ 10 mmHg
Orthostatic Hypotension	SBP St – Su ≤ - 20 mmHg DBP St – Su ≤ - 10 mmHg
Weight	≥5% increase versus baseline ≥5% decrease versus baseline
ECG parameters	
HR	≤ 50 bpm and decrease from baseline ≥ 20 bpm ≥ 120 bpm and increase from baseline ≥ 20 bpm
PR	≥220 ms and increase from baseline ≥20 ms
QRS	≥ 120 ms
QTc Borderline Prolonged* Additional	Absolute values (ms) Borderline 431-450 ms (Male) 451-470 ms (Female) Prolonged* > 450 ms (Male) > 470 ms (Female) QTc ≥500 ms Increase versus baseline (Males and Females) Borderline Δ 30-60 ms Prolonged * Δ > 60 ms

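### Adolescent height is summarised only as raw centimetres and raw change; in a single-arm study it needs a height-for-age z-score to be read against normal growth

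*SAP*

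**What the plan says.** - **Variable.** SAP 4.8.3: "Vital signs parameters will include height (cm), weight (kg), heart rate (bpm", followed by the other vital signs. Both the actual value and post-baseline minus baseline are to be provided.
- **Summary.** SAP 5.8.4: "The vital sign actual values and change from baseline values obtained while sitting will be descriptively summarized at baseline" and at each post-baseline visit, with the usual descriptive statistics, repeated for adolescents.
- **Flag.** In SAP 10.4 weight has a criterion ("≥5% increase versus baseline", and the matching decrease). Height has none.
- **Who is measured.** Protocol 8.1.3, footnote 6 to Table 3, limits post-baseline height to patients under 18. Table 3 schedules it at baseline, week 24, each visit F, end of treatment and end of study.
- **Design and objective.** SAP 2.1: "This is an open-label, single armed study designed to evaluate the long-term safety and efficacy of evinacumab in patients with HoFH". Long-term safety in adolescents is one of the two primary objectives (Protocol 2.1). About 14 adolescents are planned (Protocol 10.2), and participation may last up to about 4 years (SAP 2.3).
- **Columns.** SAP 5 splits results into Continue, New and Total, and "the three evinacumab treatment exposure groups will be provided again for the subpopulation of adolescent patients", provided there are enough of them.
- **Baseline.** For R1500-CL-1629 participants, SAP 6.1: "baseline is defined as the last obtained value before the first dose of double-blind study drug in R1500-CL-1629". All others use the last value before the first dose in this study. SAP 5.8 applies this rule to all safety analyses.

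Neither document mentions a z-score, percentile, height velocity or growth chart.

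**The concern.** Post-baseline height is taken only in patients who may still be growing, so its purpose here is to follow growth. A mean gain in centimetres does not serve that purpose unless the reader knows what gain to expect. The expected gain changes steeply through adolescence, differs by sex and rises with elapsed time, and a single-arm study has no concurrent group to supply it.

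The baseline rule adds a second problem. A visit labelled week 24 covers a longer span of growth in an R1500-CL-1629 rollover than in a naïve patient, and Total averages the two. New has a single baseline rule and no pooling problem, but it still has no reference.

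At stake is whether one safety variable, collected specifically for adolescents, can inform a primary objective. The lipid endpoints and the adverse event summaries are unaffected.

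**Working it through.** The plan gives no figure on this point to reproduce. The growth times below come from the documents. Every figure in cm or SDS (standard deviation score) rests on assumed growth curves and is illustrative.

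**1. Growth time inside the week 24 change.** Weeks are counted from the first dose in this study.
- Naïve patient: 24 weeks.
- R1500-CL-1629 rollover: 24 weeks of double-blind treatment (Protocol 1) + 24 weeks here = at least 48 weeks.
- Ratio: 48 / 24 = 2.

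The 48 weeks is a lower bound, because SAP 5.7.1 shows that R1500-CL-1629 also had an open-label period.

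**2. Normal gain by age within one 24-week interval.** Assume velocity falls linearly from v0 = 6 or 8 cm/year at age 12 to 0 at age 18. Gain from age a over T years = v0 × [(18 − a)T − T²/2] / 6, with T = 24/52.

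| Age at start | v0 = 6 | v0 = 8 |
|---|---|---|
| 12 | 2.66 cm | 3.55 cm |
| 15 | 1.28 cm | 1.70 cm |
| 17 | 0.36 cm | 0.47 cm |

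No single raw mean is the normal one, even in New.

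**3. Effect of pooling in Total.** Use the mean velocity v0/2 and let the rollover share go from 0% to 100%, with 48 weeks for rollovers.
- 3 cm/year: 3 × 24/52 = 1.38 cm to 3 × 48/52 = 2.77 cm.
- 4 cm/year: 1.85 cm to 3.69 cm.

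The effect of share is 2-fold under either velocity. The actual adolescent share is not in the documents.

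**4. Do the age and sex tables supply the reference?** Assume girls grow 5 (or 6) cm/year at 12, falling linearly to 0 at 15, and boys 7 (or 8) cm/year until 14, falling linearly to 0 at 17. Samples of 7 girls and 7 boys were drawn with ages uniform on 12 to 18. They were kept if mean age was 15 ± 0.1 and age SD 1.73 ± 0.1 (about 23,000 samples). Integrating growth over 24 weeks, the expected mean gain averages 1.12 cm (1.29 cm with the higher velocities). The central 95% of samples lie between about 0.78 and 1.23 times that average. Samples with the same sex split, mean age and age SD therefore still differ by roughly a fifth either way.

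**5. What a z-score can and cannot show.** Assume a height SD of 6 to 8 cm and a one-third slowing of growth.
- *Group, 24 weeks.* Lost height is 1.38/3 = 0.46 cm to 1.85/3 = 0.62 cm, so 0.46/8 = 0.06 to 0.62/6 = 0.10 SDS. With n = 14 and an assumed SD of z-score change of 0.2 to 0.4, the 95% half-width is 2.160 × 0.2/√14 = 0.12 to 2.160 × 0.4/√14 = 0.23. The signal is smaller than the half-width.
- *Individual.* One third of the gain from the formula in step 2, divided by 8 (low end, v0 = 6) or 6 (high end, v0 = 8):

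| Start age | Follow-up | Normal gain | Loss in SDS |
|---|---|---|---|
| 12 | 1 year | 5.50 to 7.33 cm | 0.23 to 0.41 |
| 12 | 2 years | 10.0 to 13.3 cm | 0.42 to 0.74 |
| 12 | 4 years | 16.0 to 21.3 cm | 0.67 to 1.19 |
| 15 | 1 year | 2.50 to 3.33 cm | 0.10 to 0.19 |
| 15 | 3 years | 4.50 to 6.00 cm | 0.19 to 0.33 |

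The individual benefit lies mainly in younger patients followed well beyond 24 weeks.

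**The case against.** The strongest reply is that this is a preference and not an error. Safety is descriptive by design, growth is on neither list of events of special interest, and a z-score can be derived later from stored data. Age and sex are tabulated (SAP 5.1: "The summary of demographic and baseline characteristics will be provided for all patients in the study in the safety analysis set", and again for adolescents), so a reader can look up a rough expected gain. Tanner stage, sex hormones, physical examination, adverse events and the independent data monitoring committee also watch adolescents. The SAP is a first version and may be revised before database lock.

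Much of this stands, and it is why the point is minor. The substitutes do not close the gap, however. Physical examination is scheduled only at screening, baseline and end of study, and is recorded only as clinically significant or not. Tanner stage and sex hormones are not height references, and the SAP links neither to height. The demographic tables narrow the expected gain without fixing it (step 4). That the SAP can still be revised makes the change easy; it does not supply a reference.

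Four stronger readings are tempting, and the documents do not support them:
- *Growth impairment is a suspected risk being missed.* Nothing in either document names it as a risk.
- *A normal Total mean could lie anywhere from 1.4 to 3.7 cm depending on the rollover share.* That joins the low end of one velocity assumption to the high end of another. Share alone gives 2-fold.
- *The spread is 3-fold, because rollovers who "received placebo in the DBTP but received evinacumab in the OLTP" (SAP 5.7.1) have at least 72 weeks.* That adds the 24 weeks of prior evinacumab in Protocol 3.2.3 to 24 weeks of placebo. But SAP 5.7.1 gives evinacumab-first patients an open-label period too, so if both groups completed it both intervals exceed 48 weeks. Its length is not stated.
- *Continue mixes baseline rules as well.* That needs adolescents from R1500-CL-1331, and none is documented.

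**Conclusion.** The point holds as a minor one. The planned height table reports a gain with no reference value and cannot, on its own, distinguish normal from slowed growth. In Total it also averages growth times that differ by a factor of at least 2, on the condition that both naïve adolescents and R1500-CL-1629 adolescent rollovers are enrolled and that height was recorded before the parent study's first dose.

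The missing reference and the growth times follow from the text. The centimetre and SDS sizes rest on assumed velocities, height SD and SD of z-score change, and show scale only. A reader might infer that a z-score would make slowed growth detectable in this sample. It would not for mild slowing in the group mean, as step 5 shows. Nor does 4 years of follow-up apply to everyone: post-baseline height stops at 18, so a patient enrolled after 14 cannot contribute 4 years.

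**What to change.** Keep the raw centimetre summaries. Add to SAP 5.8.4, for patients under 18 at the visit:

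1. A height-for-age z-score by sex, using age at the measurement date, against one growth reference named in the SAP.
2. Its value and change from baseline by visit, in the Continue, New and Total columns.
3. A listing of individual z-scores with Tanner stage and time since the baseline measurement, flagging falls beyond a numeric threshold fixed in advance, for example 0.5 SDS. On the assumptions in step 5, a one-third slowing from age 12 would reach that level at around 2 years or later, and one starting at 15 would not reach it, so the individual values should be read as well as the flag.

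The cost is SAP wording, one derived variable and one listing, with no new visits or measurements. One reference must be chosen for a multinational sample. SAP 4.1 gives age only in years, so the available age precision must be confirmed. The z-score does not adjust for pubertal timing, and patients below Tanner stage 2 are excluded, so an expected change of exactly 0 is not assured; hence Tanner stage belongs in the listing. Fixing the reference and threshold before results are seen is the reason to do this now instead of deriving it later.

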4.8.5. Physical Examination Variables

Physical examination will be conducted at the protocol scheduled visits (See Appendices 10.5 and 10.6 for schedule of events). The result is an outcome of clinically significant (Yes/No, not examined) and visits will be assigned to the Global Analysis Windows (See Appendix 10.2).

Tanner assessments for boy and girl will be conducted at the protocol scheduled visits (See Appendices 10.5 and 10.6 for schedule of event).

4.9. Other Variables

Other assessment endpoints are listed and defined below. Protocol schedule visits will be assigned to the Global Analysis Windows (See Appendix 10.2).

- The change in hemoglobin A1c (HbA1c [%]) from baseline to post-baseline visits.
- The percent change in hs-CRP from baseline over time.
- The percent change in HDL-C from baseline over time
- The percent change in Apo A1 from baseline over time
- The percent change in Apo B/Apo A1 ratio from baseline over time
- The percent change in Lp(a) from baseline over time
- The percent change in Apo CIII from baseline over time

4.10. Pharmacokinetic Variables

Pharmacokinetic (PK) variables include total evinacumab concentrations and total ANGPTL3 concentrations collected at each specified time point.

4.11. Immunogenicity Variables

Anti-drug antibody variables will include ADA status, titer and neutralizing antibody (NAb) status and time-point/visit. Serum samples for ADA will be collected at the clinic visits specified in Appendices 10.5 and 10.6.

5. STATISTICAL METHODS

In general, data will be summarized and presented in three patient groups, depending on the status of previous evinacumab treatment exposure:

- Continue Evinacumab: Patients who received evinacumab in a previous study (eg, R1500-CL-1331 or R1500-CL-1629);
- New Evinacumab: Patients without previous exposure to evinacumab (ie, evinacumab naïve);
- Total: All patients, regardless of previous (or not) evinacumab exposure.

These 3 evinacumab exposure groups will be provided for all patients in the respective patient analysis sets. Assuming there are enough adolescent patients (age ranging from 12 years to < 18 years old) to perform an evaluation, the three evinacumab treatment exposure groups will be provided again for the subpopulation of adolescent patients [yes/no]. The subpopulation of adolescent patients has two categories, specifically the patient is an adolescent defined as ranging in age from 12 years to < 18 years old, or the patient is not an adolescent (i.e. an adult) defined as ≥ 18 years of age. Unless otherwise noted, data from both adolescent and adult patient subgroups will be summarized.

Continuous data will be summarized descriptively using the number of patients with data, mean, SD, median, minimum and maximum for each patient group for the study. First quartile (Q1) and third quartile (Q3) will be also provided for baseline lipid parameters, HbA1c, and hs-CRP.

Categorical and ordinal data will be summarized using the number and percentage of patients for each patient group for the study.

5.1. Demographics and Baseline Characteristics

Demographic and baseline characteristics will be summarized descriptively by patient group for the study in the safety analysis set.

Parameters listed in Section 4.1 will be summarized as described. As applicable, other safety baseline data not listed in Section 4.1 will be presented collectively in the descriptive statistics summary tables containing respective post-baseline data.

The summary of demographic and baseline characteristics will be provided for all patients in the study in the safety analysis set, and again for the subpopulation of adolescent patients.

5.2. Medical History

Medical history will be descriptively summarized by patient group for the study in the safety analysis set, and again for the subpopulation of adolescent patients [yes/no].

All reported patient's medical history will be presented by primary SOC and HLT. The tables will be presented by SOC sorted alphabetically and decreasing patient frequency of HLT based on the overall incidence in the study.

In addition, all medical history of specific interest, primary and secondary CVD prevention including corresponding criteria, as described in Section 4.2, will be summarized by patient incidence and percentage.

The number (%) of patients will be summarized by CVD prevention status (i.e. primary and secondary CVD prevention status).

In addition, smoking and alcohol consumption status will be summarized in patients with primary CVD prevention status.

For patient disease characteristics, as described in Section 4.2, continuous data will be summarized using the number of patients with data, mean, SD, median, Q1, Q3, minimum and maximum for the study and for each of the patient groups. Categorical and ordinal data will be summarized using the number and percentage of patients in the study and for each of the patient groups.

